Step 2. We surveyed the country with guidance from Ministry of Health publications and consultations, and excluded districts that have or recently had an active maternal health or newborn health intervention, as this would dilute the effect of our intervention or result in high levels of quality of birth care at baseline, with little room for improvement.

Step 3 We combined Western and Southwest Regions into one group and Eastern and East Central Region into a second group in order to consolidate as Western had only 4 possible districts and East Central had only 3.

Step 4. We examined the a) number of facilities by type in each district and b) caseload of births in one year (July 2012- June 2013) in each district, and calculated the average number of births per facility per day. We then selected all districts within the two groups that had an average of > or = to one birth per facility per day. This resulted in 6 districts in the Eastern group and 6 in the Western group.

All public Level II, III, and IV facilities offering birthing services within a district will be included (range of 7-17 per district for a total of 133 facilities). In districts where there is no public hospital, we will include any Private Not for Profit hospital providing birthing services in that district where they exist. In all of these facilities, as mentioned in Section 3c, an estimated 1,300 providers will be included in the study.

District assignment to intervention arm:

In each region we will divide the six districts into two groups of three. Within the groups of three we will randomly choose a district name from a hat. For the district pulled we will draw a number card with a “1”, “2”, or “3” from a hat. Those numbers will correspond with the study arms outlined in Table 1 (page 2).

- Describe the study participants and the population from which they will be/were drawn. If you plan to include children, specify their ages and gender.

Study participants include any providers at selected facilities who provide birthing services to women and all women admitted to the labor ward for labor. (Table 2 presents the maximum number of study contacts per participant.

Table 2. By research objective, Participants (Sample and Population), Data Source, and Number of Contacts

Obj.	Study Participants (Sample & Population)	Data Source	Number of Study Contacts

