The study is a quasi-experimental design with three study arms/groups that receive different levels or intensities and modalities of the program intervention. Figure 1 (page 10) provides an overview of the intervention and evaluation components of the study. Briefly, the same simulator-based training will be provided in all three study arms. After the training, a simulator will be left in the health facility, and providers will be encouraged to practice with it regularly. In two of the study arms, specific health workers will be recruited to support the intervention by encouraging their colleagues to practice with the simulator. In one study arm, the practice will be further reinforced through mobile phone-based support. Following is a more detailed description of each of the three components.

Component 1 (Training): Training is composed of two separate training interventions. First, in each study facility, we will conduct a single day, simulator-driven training on PPH prevention and treatment; all providers who attend births will be invited to participate. Eight weeks later, in each facility, we will conduct a one-day, simulator-driven training for prevention and management of asphyxia in the newborn. After each one-day training, simulators will be left at the facility for practice with a corresponding practice schedule.

Component 2 (Peer-led Practice Sessions): On the day the first training (for PPH), 2 birth attendants at the facility will be selected to serve as peer practice coordinators (PPC). The PPCs will be trained to encourage their coworkers to participate in 15-minute practice sessions each week for 8 weeks, in which they will use the simulators to practice the skills learned in the one-day training. After the newborn asphyxia training occurs, these same PPCs will be trained to support a similar practice schedule for the following 12 weeks - 8 weeks for newborn asphyxia practice and 4 weeks for combined PPH and asphyxia skills practice.

Component 3 (Mobile phone-based support): (Note: This component is being negotiated with the ministry of health in conjunction with UNICEF due to the moratorium on mHealth interventions) Labor ward providers will be given mobile text messages for:

- 1) Content reminders
- 2) Practice reminders

[figure not shown]
PPCs will be connected to the district trainer via mobile phone for weekly phone calls during the practice periods to provide reminders and support for practice.

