2. Provider competencies and performance will not decline (i.e. will be non-inferior) between midline and endline in the *partial* package group.
3. At endline, the provider competency level and the performance level of the *partial* package group will be significantly higher than those of the training-only group.
4. At endline, the provider competency level and the performance level of the *full* package group will be significantly higher than those of the training-only group.

Hypotheses 1 and 2:

This is a non-inferiority analysis. Two-sided 90% confidence intervals (CI) for the difference in average knowledge and competence scores between midline and endline will be constructed, separately for full and partial package groups. Non-inferiority will be determined comparing the upper bound of the 90%CI for the difference between the 2 time points to the pre-specified non-inferiority margin of 0.06 (22). If the CI's upper bound is less than the predefined margin, then we are able to claim non-inferiority of the endline knowledge scores to the midline knowledge at a 0.05 level of significance.

We will first examine the differences in sample means of knowledge scores between midline and endline not adjusted for any potential confounding variables. The confidence intervals for the knowledge scores will be calculated using generalized linear models with knowledge and competencies as the dependent variables and time variable (endline vs. midline) as the primary independent variables. To account for repeated observations within providers at midline vs. endline, we will use robust Huber/White estimate of variance implemented in STATA through 'vce' (cluster) option. In addition, adjusted 90% CI for the difference in means will be constructed by adding provider- and facility-level factors in the model.

Hypotheses 3 and 4:

We will examine differences in competencies and performance at endline between the 3 study groups using generalized linear models. The dependent variables in these models will be:

- 1) knowledge and competency scores,
- 2) proportion of women who received **oxytocin** (at correct dosage) within one minute of a vaginal birth,
- 3) proportion of women whose placenta was inspected within 16 minutes, and
- 4) proportion of newborn checked for breathing within 1 minute.

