The primary independent variable will be the study group represented as 2 indicator variables for full and partial training package with training-only as the reference group. For these hypotheses, we will only use endline data. Additional variables, related to provider- and facility characteristics predictive of these outcomes, such as cadre, number of years of provider's experience, and number of prior births attended in last 90 days, will be also included in the model. Analysis of residuals will inform whether the assumptions of the generalized linear model, such as normality and homoscedasticity of residuals as well as linear fit, are satisfied.

Additional analyses will include:

1. At baseline, midline and endline we will collect data from **all study facilities** consisting of service delivery statistics, and facility inventory. These data will be analyzed using population-average marginal generalized linear models estimated using generalized estimating equations (GEE) with exchangeable working correlation structure to account for repeated observations within facilities. The dependent variable will be service delivery statistics. The independent variables will include time (represented as 2 indicator variables for midline and endline with baseline as the reference group), study group (represented as 2 indicator variables for full and partial training groups with training-only as the reference group), and interaction terms (study group by time). The interaction terms will be examined to assess whether there are differences between study groups that change significantly over time.
2. Providers who are trained will keep **logs of their practice sessions**. This is process evaluation data. These data (for example on number of times a scenario is practiced) will be compared across the three study groups using generalized linear models with Poisson or Negative Binomial distribution for the outcome.
3. **Routinely collected data from health facility registers** (recorded daily but aggregated monthly) on services provided to clients and health outcomes (discharge, or deaths and stillbirths) will be analyzed using longitudinal data analysis to account for repeated observations at each facility. This will be for population-averaged marginal generalized linear models using generalized estimating equations (GEE) and exchangeable working correlation structure.

Qualitative Analysis

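### Hypotheses 1 and 2: the score intervals allow for repeat tests within providers but state no facility-level clustering, so they can be too narrow if score change differs between facilities

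*Combined protocol and SAP*

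**What the plan says.** Section 4b5 (Hypotheses 1 and 2) sets the decision rule for knowledge and competence scores, separately in the full and partial package arms: "Two-sided 90% confidence intervals (CI) for the difference in average knowledge and competence scores between midline and endline will be constructed". The upper limit is compared with a "pre-specified non-inferiority margin of 0.06". If it falls below, the plan states that "we are able to claim non-inferiority of the endline knowledge scores to the midline knowledge at a 0.05 level of significance".

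The variance method has one stated purpose: "To account for repeated observations within providers at midline vs. endline, we will use robust Huber/White estimate of variance implemented in STATA through" a cluster option. The clustering variable is not given. Facility enters only through covariates in a supplementary analysis: "adjusted 90% CI for the difference in means will be constructed by adding provider- and facility-level factors in the model".

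The intervention runs by facility. Under Component 2 in Section 4b1, "2 birth attendants at the facility will be selected to serve as peer practice coordinators (PPC"). Simulators are left at each facility, and assessment takes place during a visit of two or three days to each facility (Section 4b2). Section 3 gives the number of facilities as a "range of 7-17 per district for a total of 133 facilities".

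Elsewhere the plan does allow for facilities. Table 5, notes (a) and (b), uses an ICC for births, and items 1 and 3 of the additional analyses in Section 4b5 use GEE for repeated observations within facilities.

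**The concern.** Providers at one facility share coordinators, simulators and an assessment visit. After midline the active intervention stops, and whether practice goes on is likely to be settled facility by facility. The protocol expects facilities to diverge: Table 6 sorts them into high and low adherence, and the qualitative analysis contrasts those that practise with those that do not. If scores hold up in some facilities and fall in others, the changes of colleagues are correlated, and clustering on provider counts them as independent.

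The direction of the error matters. Non-inferiority is claimed when an upper limit lies below a margin. A standard error that is too small pulls that limit down, so a true decline as large as the margin would pass more often than the stated 0.05. The conclusion that skills last without support feeds the scale-up recommendations to government described in Section 4b10.

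**Working it through.** **Inputs from the documents**
- Two-sided 90% interval, margin 0.06, stated level 0.05 (Section 4b5).
- 651 providers per assessment, described as a maximum (Section 3c, Table 3); 133 facilities (Section 3). 651/133 = 4.9 per facility.
- A second count of about 1,300 providers (Section 3). 1,300/133 = 9.8 per facility.
- ICCs of 0.005 and 0.01, for births only (Table 5 notes).

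**Assumptions**
- The facility ICC of the midline-to-endline change in score, written ρ. The documents give none, so a range is shown.
- An equal split of facilities, 133/3 ≈ 44 per arm.
- Clustering on provider, which is inferred from the stated purpose.

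**Step 1: the plan's own figure.** α = (1 − 0.90)/2 = 0.05. This reproduces exactly, provided the standard error is right.

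**Step 2: facilities in the births calculation.** Non-inferiority at 70% against 70%, margin 0.10, one-sided 0.025 and 80% power needs 330 births per time point. With ICC 0.005 and 54 facilities, 330 × (1 + 6 × 0.005) = 340; 340/54 = 6.3, rounded up to 7; 7 × 54 = 378, as in Table 5. For the endline comparison, 50% against 65% needs 170 per group. With ICC 0.01 and 27 facilities (27 is inferred), 170 × (1 + 6 × 0.01) = 180; 180/27 = 6.7, rounded up to 7; 7 × 27 = 189, also as in Table 5. The plan therefore allows for facilities in the births but states no such allowance for the scores.

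**Step 3: effect on the score decision.** With m providers per facility, all tested twice, the variance of the mean change is multiplied by DE = 1 + (m − 1)ρ. If the standard error ignores this, a true decline equal to the margin passes with probability 1 − Φ(1.645/√DE). The correct interval is √DE times as wide.

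| Change ICC ρ | DE (m = 4.9) | Width ratio | True α | DE (m = 9.8) | Width ratio | True α |
|---|---|---|---|---|---|---|
| 0 | 1.000 | 1.00 | 0.050 | 1.000 | 1.00 | 0.050 |
| 0.005 | 1.019 | 1.01 | 0.052 | 1.044 | 1.02 | 0.054 |
| 0.01 | 1.039 | 1.02 | 0.053 | 1.088 | 1.04 | 0.057 |
| 0.05 | 1.195 | 1.09 | 0.066 | 1.439 | 1.20 | 0.085 |
| 0.10 | 1.389 | 1.18 | 0.081 | 1.877 | 1.37 | 0.115 |
| 0.20 | 1.779 | 1.33 | 0.109 | 2.755 | 1.66 | 0.161 |

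Table 3 is a maximum. If 3.5 providers per facility were tested (assumed), DE at ρ = 0.05, 0.10 and 0.20 would be 1.125, 1.25 and 1.50, and α would be 0.060, 0.071 and 0.090.

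**Step 4: simulation with provider turnover.** This used 44 facilities, 5 or 10 providers each, 100%, 70% or 50% of providers tested at both times, a true decline equal to the margin, and 4,000 runs per setting. The variance components are assumed. Error rates with provider-level clustering were:
- Facility effect stable over time: 0.051 to 0.054 if everyone is tested twice, 0.043 to 0.044 at 50% overlap.
- Facility-by-time variance 1% of the total (ρ about 0.02): 0.048 to 0.065.
- 5% (ρ about 0.09): 0.07 to 0.11.
- 10% (ρ about 0.17): 0.09 to 0.145.

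Facility-level clustering gave 0.05 to about 0.06 in every setting.

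**The case against.** A reader might infer that the intervals must be too narrow simply because practice is organised by facility. That does not follow. Hypotheses 1 and 2 compare the same facilities at two times, so a lasting difference between facilities drops out. With stable facility effects, provider-level clustering is about right when all providers are tested twice, and slightly conservative at 50% overlap. Only variation in the change between facilities does harm. This objection stands, and it makes the concern conditional.

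The size is also uncertain. At the plan's own births ICCs the excess is trivial at 4.9 providers per facility (0.052 to 0.053). Those ICCs describe births rather than score change over a period without support, so they neither establish the problem nor rule it out.

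A reader might also take the plan to specify provider as the cluster variable. It does not name one; provider is the natural reading of a section that presents itself as brief.

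Finally, a reader might extend the criticism to the practice logs, which "will be compared across the three study groups using generalized linear models with Poisson or Negative Binomial distribution for the outcome". The documents do not support that. The unit of analysis is not stated, and the log is a form kept by the facility's coordinators. If each facility contributes one count, there is nothing to cluster within facility. The point would arise only if counts were analysed per provider.

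**Conclusion.** The concern holds in conditional form. The plan states no facility-level allowance for the Hypothesis 1 and 2 score intervals. If score change varies by facility, provider-level clustering gives intervals that are too narrow and a one-sided error above 0.05. At 4.9 providers per facility the error reaches about 0.08 at a change ICC of 0.10; at 9.8 it is already about 0.085 at an ICC of 0.05. At ICCs of 0.005 to 0.01 it is negligible for the smaller facility size and 0.054 to 0.057 for the larger. These figures rest on an assumed ICC, on facilities of equal size, and on the inferred provider cluster variable.

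It should be fixed before analysis but is not critical. Section 4b5 lists score change as a secondary outcome, and this interval does not address the two primary outcomes, observed oxytocin use and newborns breathing or ventilated by one minute.

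**What to change.** In Section 4b5, Hypotheses 1 and 2, name facility as the cluster variable, in Stata vce(cluster facility), for both the unadjusted and the adjusted interval. This also covers repeat tests of providers who stay at one facility. Providers who move between study facilities are not fully covered, so report how many there are. About 44 facilities per arm were enough in the simulation. The split may be unequal: four districts of 7 to 17 facilities could hold anywhere from 28 to 68.

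State as a limitation that facility clustering does not cover change shared by a whole district. Arms are assigned by district, with 12/3 = 4 per arm, so show the change by district beside the main result. Such a display describes district variation but does not correct the error rate for it.

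For the practice logs, state the unit of analysis; if counts are per provider, cluster on facility there too.

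The cost is one added term in the plan and one Stata option, with no new data. Intervals may widen, by 1% to 33% over the ICC range shown at 4.9 providers per facility.

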- **Inclusion Criteria:** Women in any stage of labor in participating facility who consent to observation of their delivery and care of their newborn (or consent from the next of kin if the woman is incapacitated and not able to provide consent)
- **Exclusion Criteria:** none

Facility In-charges and Stakeholders

- **Inclusion Criteria:** Facility in-charges at sampled health facilities; stakeholders identified by Jhpiego senior managers as being influential in maternal and newborn health policy decisions in Uganda.
- **Exclusion Criteria:** none

c. Provide **sample size** and a **justification** as to how you arrived at your projected sample size.

The total sample size for this study is 4683 - 2604 health care providers plus 2079 laboring women.

Knowledge and Competency Assessments

For the knowledge and clinical practice assessment, we propose conducting a census of birth attendants working at each facility on the days of training and midline and endline facility data collection. In training interventions, it is routine to test participants before and after the intervention in order to give them feedback to clarify any misunderstandings and improve their performance. We will also do these assessments at baseline and midline facility data collection because we are also interested in collecting data from all providers so that we can do a secondary analysis that will test for a correlation between providers' performance on knowledge assessments and simulator-based performance tests, participation in practice sessions, and directly observed clinical performance. Table 3 presents the maximum number of providers in

the sample facilities, based on data provided by the Ministry of Health; actual enrolled numbers will be lower because not all health care providers on staff will present on the day of data collection. **In addition, we recognize there will be overlap between providers at each time point.** The outcome measure will be a continuous variable measuring ‘correct’ knowledge and competencies across three OSCE exams of BAB or HBB.

Table 3. Number of Providers to be Assessed (c)

Region	Pre and post BAB training (a)	Pre and post HBB Training (a)	Midline Assessment (b) (d)	Endline Assessment (b) (d)	Total Providers in each study group (e)
Districts in Eastern	253	253	253	253	1012
Districts in Western	398	398	398	398	1592
Grand Total	651	651	651	651	2604

Notes

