Service statistics for deliveries and newborn care will be collected from the monthly aggregate reports that do not have the client names (no identifiers).

Providers:

Identifiers will be collected from health providers observed in clinics and/or trained. Provider identifiers will be stored in a database that will be separate from the database storing information about provider knowledge and performance. Rationale: We will follow individual providers over time to track increase in performance or competencies. We need to be able to identify unique providers, such as by collecting name, date of birth, cadre, and health facility, in order to link the data collected on the same provider at various time points (longitudinal analysis). In one study arm providers will be invited to share their mobile telephone number in order to receive content and practice reminders. We will collect no identifiers from providers that participate in focus group discussions.

Facility in-charges and stakeholders:

We will collect no identifiers from those asked to participate in the semi-structured interviews.

Does your study fall within HIPAA requirements because of either of the following:

- 1) The study team will access, collect, and/or use for research purposes protected health information disclosed by a U.S. health care provider (covered entity), or
- 2) Identifiable private health information collected elsewhere (including from a foreign country) will be brought to a covered entity here in the U.S. (for example, a JHU SOM laboratory) for analysis?

No. Jhpiego is not a covered entity because it does not provide health care, health insurance or services related to health care billing.

4. Study procedures:

- b.** If your study involves contact, direct or indirect, with subjects, provide the following:
 - 1) General **study design and methods.**

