2) **Study procedures, including sequence and timing.**

Figure 1 presents an overview of activities related to the intervention and its evaluation.

Figure 1 – Intervention and Evaluation Activities

Saving Lives on the Day of Birth: Building and Sustaining Capacity of Frontline Health Workers in Uganda

Intervention Description – More Detailed

Intervention: Bleeding After Birth

The intervention starts with all study arms receiving a one-day, facility based PPH prevention simulator-assisted training of all providers who attend births in a facility with the simulators being left onsite for ongoing practice:

The first module of the twinned training, “Bleeding after Birth” (BAB), uses graphic materials and simulation, to teach providers psychomotor and decision making skills to prevent, detect, and manage PPH including both treatment and timely referral as appropriate. To ensure retention and improved performance, for two of the study arms training will be followed by ongoing **low dose, high frequency (LDHF) simulation practice** conducted by Peer Practice Coordinators at the facility. (The “training-only” study arm will have the PPH simulator left at the facility with a recommended schedule for practice, but no PPCs designated to coordinate the training.) PPCs will be providers already posted at the facility who have undergone the training and have agreed to take on the role to support ongoing training in their facilities. After the initial training module is delivered, two providers per facility will be invited to participate in improving care for PPH and newborns by become PPCs. Two will be selected to address turnover and ensure simulated practice is conducted on a routine basis. After training in the first module (BAB), the PPCs will undergo a half-day training to enhance their skills related to peer-led training.

To test the added value of **mobile phone support**, providers or PPCs in one of the two intervention arms receiving the PPC LDHF intervention will receive ongoing SMS and voice support during the LDHF practice period. PPCs will be provided ongoing mobile support as reminders for practice and to maintain their clinical and training-related capacities. This technology will be used to provide remote reinforcement, assessment and real-time performance support by master trainers to PPCs. In addition, SMS messaging will be used for providers in this intervention arm to provide clinical content and practice reminders.

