 - Designated Peer Practice Coordinators (PPC) will log their weekly practice sessions on logs (full and partial arms only).
 - Data on the number of reminders that are sent to providers will be recorded, along with logs of calls between trainers and PPCs (full arm only).
 - Aggregated HMIS data related to PPH, newborn care and mortality data will be collected from routine and supplemental HMIS forms.
- When the five months of the active intervention phase is over, then there will be a midline assessment of providers and facilities: this will again involve a facility assessment, provider knowledge test and OSCEs, observation of provider performance, and qualitative data collection at some facilities. This will take place over 2 or 3 days.
- During the same time period, the research team will contact stakeholders by telephone to schedule interviews with them. Then the interviews will be conducted at the stakeholders' offices or another location, if requested by the stakeholder.
- Following the midline assessment, there will be a 'dormant' phase of no active intervention. This is to determine if competencies and performance is maintained by low-dose high-frequency practice in the absence of donor support. We will return six months later for an endline assessment, which is the same as the midline assessment except there will be no qualitative component.

Table 7. – Description of Data Collection Instruments

Tool #	Title	Content
1	Health Worker Listing	Name and cadre for each health worker at each facility. This will be used to generate a unique ID for each provider
2	Facility Inventory	Information about the tools and equipment available at the facility related to the study intervention, such as the availability of uterotonic drugs and neonatal resuscitators.
3	Direct clinical observation tool	Structured checklist that observers will use to take notes on the care provided to women and neonates, including routine care and treatment for postpartum hemorrhage or neonatal asphyxia.
4	Supplemental maternity register	Note: We will provide this register to facilities, but Jhpiego researchers will not abstract individual records from this document (facility staff will do this). This register collects data about each birth that is relevant to this study, such as whether a woman was diagnosed with postpartum hemorrhage and whether a newborn received bag & mask resuscitation.

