Provider identifiers will be disposed of 1 year after the project end date. Any paper-based data recordings will be shredded. The electronic files will be deleted.

d. Describe any plans for **destroying data** including if, when and how that will be done. JHU policy states that the PI is the steward of research data and is responsible for all information (recorded on any media) and materials (biological or environmental samples) (see: http://jhuresearch.jhu.edu/Data_Management_Policy.pdf.) This responsibility includes physical custody and/or control of the data, storage and sharing (with data use agreements).

Hard copies of data and electronic recordings of focus group discussions and interviews will be disposed of 1 year after the project end date. Electronic databases without any provider identifiers will remain and will not be destroyed, for possible future additional analyses.

6. Recruitment process:

a. Describe how, and from where, **participants will be recruited**.

All participating providers offering services on the day of birth approved by the facility in charge will be invited to participate in the study. Some providers will be identified by the district authorities and invited to the training on Bleeding After Birth and Helping Babies Breathe. Other providers may learn from those trained providers and be observed by our study.

Peer practice coordinators will be identified by the facility in-charges and district officials from each participating district, and the providers identified will be invited to participate as a PPC. They will receive special training for their PPC role.

Women in labor at the facilities on the days of observation will all be invited to participate. We will approach them in the facility. Data collectors will wait in the maternity ward. They will be approached after they have been admitted for delivery care. Women will be approached at the bedside, as soon as possible, to avoid enrolling women in advanced labor. If they are in the second stage of labor, experiencing a complication, or otherwise in distress, we will seek consent from the person that accompanied them.

Stakeholders will be identified based on the knowledge of Jhpiego/Uganda leadership and in consultation with the Uganda Ministry of Health. They will be contacted at their place of work in person and asked to participate in the study.

b. Explain how your **recruitment materials** will be used.

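### The midline-to-endline competency test compares two partly different groups of staff, so its estimate can mix skill retention with change of staff

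*Combined protocol and SAP*

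**What the plan says.** **Who is tested.** Section 3c (Knowledge and Competency Assessments) states: "we propose conducting a census of birth attendants working at each facility on the days of training and midline and endline facility data collection". It accepts that "not all health care providers on staff will present on the day of data collection" and adds that "we recognize there will be overlap between providers at each time point", without a figure. Table 2 describes those tested as birth attendants present on training days, assessment days or both. Section 3b lists no exclusion criteria for providers. Training is therefore not a condition of being assessed.

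**Turnover.** Section 4b2 gives the reason for appointing a pair of peer practice coordinators per facility: "Two will be selected to address turnover and ensure simulated practice is conducted on a routine basis". No turnover rate is given. After midline comes a phase without active intervention, and then: "We will return six months later for an endline assessment".

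**The test.** For Hypotheses 1 and 2, Section 4b5 starts from an unadjusted difference in mean scores, estimated by a generalized linear model with time as the main regressor. A two-sided 90% confidence interval is set against a margin of 0.06, separately for each of the two arms. Repeated providers are handled as follows: "To account for repeated observations within providers at midline vs. endline, we will use robust Huber/White estimate of variance". A further interval adjusts for provider and facility factors that are not named for these hypotheses.

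**Linkage.** Section 3d explains why provider identifiers are collected: "We will follow individual providers over time to track increase in performance or competencies". It names longitudinal analysis as the purpose of linking records.

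**The concern.** Hypotheses 1 and 2 claim that competency does not decline over the dormant phase. A cluster-robust variance changes the standard error and leaves the estimate alone, so the tested quantity remains the mean of those present at endline against the mean of those present at midline. If some providers leave and others join, the difference contains both the change in retained providers and the difference between leavers and joiners.

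These are before-after comparisons within one arm, so no comparison arm subtracts the staff change. Lower-scoring joiners could make a workforce that kept its skills fail the test. Higher-scoring joiners could hide a real decline. The data needed to separate the two are already being collected, but the planned estimate does not use them.

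**Working it through.** **The plan's own figure.** A two-sided 90% interval leaves (1 − 0.90)/2 = 0.05 in each tail, which matches the stated 0.05 level. No sample size, SD or power is stated for this test. The only non-inferiority sample size in Section 3c concerns observed oxytocin use, with a margin of 0.10.

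**Inputs from the documents.** Margin 0.06, read here as 6 points on a proportion-correct scale. Interval between visits: six months. At most 651 providers per assessment round (Table 3).

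**Assumed, because the documents are silent.** Share of endline assessees who replace midline assessees, f: 10 to 30%. Score gap, g: 10 to 30 points. SD: 0.15 or 0.20. Within-provider correlation: 0.5. Equal arms: 651/3 = 217. Facility clustering is ignored, so the standard errors below are probably too small.

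**Step 1: what the difference estimates.** Let δ be the mean decline in providers seen at both visits. Let g be the amount by which joiners score below what leavers would have scored at endline with that same decline. Then midline minus endline = δ + f × g. With δ = 0 the difference is f × g alone.

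**Step 2: size of the shift, in points.**

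| f | g = 10 | g = 20 | g = 30 |
|---|---|---|---|
| 10% | 1 | 2 | 3 |
| 20% | 2 | 4 | 6 |
| 30% | 3 | 6 | 9 |

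Three of the nine cells reach the 6-point margin. The gap needed to use it all is 0.06/f: 60 points at 10%, 30 at 20%, 20 at 30%.

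**Step 3: effect on the decision.** A smaller shift can matter, because the interval's half-width takes part of the margin. With SE = √[2 × SD²/217 × (1 − (1 − f) × 0.5)], the chance of claiming non-inferiority is Φ((0.06 − f × g)/SE − 1.645). For f = 20%, g = 0.20 and SD 0.15, SE = 0.0112 and Φ(0.02/0.0112 − 1.645) = 0.56. With no decline in any retained provider:

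| f, g | SD 0.15 | SD 0.20 |
|---|---|---|
| 0 | 1.00 | 1.00 |
| 10%, 20 points | 0.98 | 0.88 |
| 10%, 30 points | 0.88 | 0.68 |
| 20%, 20 points | 0.56 | 0.38 |
| 20%, 30 points, or 30%, 20 points | 0.05 | 0.05 |

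**Step 4: the opposite direction.** Take a true decline of 0.06, 80% overlap and SD 0.15. If joiners outscore leavers by 20 points, the composition term is −0.04 and the net difference is 0.02. The chance of a false claim rises from 0.05 to 0.97.

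**Step 5: the matched alternative.** Among providers seen at both visits the composition term is zero by construction. With 70% overlap there are 0.70 × 217 ≈ 152 pairs, and with correlation 0.5 the SE is SD/√152. The 90% half-width is about 0.020 (SD 0.15) or 0.027 (SD 0.20). Power with no true decline is above 0.99 or about 0.98.

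**The case against.** The strongest reply is that the target may be the facility's current workforce. The study title speaks of sustaining capacity, the paired coordinators answer turnover, and the dormant phase asks what lasts without donor support. On that reading staff change is part of the result and the census comparison is legitimate. This stands as a possible reading. But the plan does not state it, and the reason given in Section 3d for collecting identifiers points to individual providers.

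A reader might infer that untrained newcomers will be in the endline tests. The documents permit this but do not say it. The explicit line in Section 6a, "Other providers may learn from those trained providers and be observed by our study", concerns observation of care, not the knowledge and skills tests. Nor can one say that the adjusted analysis omits training status: its factors are unspecified, and the examples in Section 4b5 (cadre, experience, recent births) belong to Hypotheses 3 and 4.

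The gap may also be modest. All public Level II to IV facilities offering births in a district are included and arms are assigned by district, so someone transferring within a district may already have had the same training in the same arm. Staff absent because of the duty roster were probably trained as well. True turnover therefore matters more than who happens to be on shift.

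**Conclusion.** The concern holds in a limited form. The planned estimate can mix retention with staff change, in either direction, and the plan does not say which of the two questions it means to answer. Whether this matters in practice depends on turnover and score gaps that the documents do not give.

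It would be tempting to conclude that turnover will decide non-inferiority. The documents do not support that. The whole margin goes only at combinations such as 20% with 30 points or 30% with 20 points. At 10% turnover or less, composition alone would not plausibly use it up, although a large gap would still lower the chance of a claim. The probabilities above rest on an assumed n, SD and correlation and are illustrative.

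The point concerns knowledge and competency scores, which Section 4b5 lists as secondary. It does not bear on the non-inferiority calculation for oxytocin use.

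**What to change.** In Section 4b5, pre-specify for the retention claim in Hypotheses 1 and 2 a within-provider analysis of those assessed at both midline and endline, by paired difference or provider fixed effect, against the existing 0.06 margin. Keep the all-present comparison beside it as the result for the facility workforce, and state which conclusion each supports. Report by arm the numbers of leavers and joiners and the joiners' training status. List the adjustment factors for these hypotheses.

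This is a cheap improvement: it changes analysis wording and uses IDs already planned. There are two costs. The matched test has fewer providers, and it describes only staff who stay and are present, which is the reason to keep the census result. Under the assumptions above, the loss of precision looks affordable.
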